## **10.3. Appendix 3: Adverse Events: Definitions and Procedures for Recording, Evaluating, Follow-Up, and Reporting**

### **10.3.1. Definition of AE**

AE Definition

• An AE is any untoward medical occurrence in a patient or clinical study participant, temporally associated with the use of study intervention, whether or not considered related to the study intervention.

• Note: An AE can therefore be any unfavorable and unintended sign (including an abnormal laboratory finding), symptom, or disease (new or exacerbated) temporally associated with the use of study intervention.

Events Meeting the AE Definition

• Any abnormal laboratory test results (hematology, clinical chemistry, or urinalysis) or other safety assessments (eg, ECG, radiological scans, vital sign measurements), including those that worsen from baseline, considered clinically significant in the medical and scientific judgment of the investigator. Any abnormal laboratory test results that meet any of the conditions below must be recorded as an AE:

• Is associated with accompanying symptoms;

• Requires additional diagnostic testing or medical/surgical intervention;

• Leads to a change in study dosing (outside of any protocol-specified dose adjustments) or discontinuation from the study, significant additional concomitant drug treatment, or other therapy.

• Exacerbation of a chronic or intermittent preexisting condition, including an increase in either frequency and/or intensity of the condition.

• New condition detected or diagnosed after study intervention administration, even though it may have been present before the start of the study.

• Signs, symptoms, or the clinical sequelae of a suspected drug-drug interaction.

• Signs, symptoms, or the clinical sequelae of a suspected overdose of either study intervention or a concomitant medication. Overdose per se will not be reported as an AE or SAE unless it is an intentional overdose taken with possible suicidal/self-harming intent. Such overdoses should be reported regardless of sequelae.

#### Events NOT Meeting the AE Definition

- Any clinically significant abnormal laboratory findings or other abnormal safety assessments that are associated with the underlying disease, unless judged by the investigator to be more severe than expected for the participant's condition.
- The disease/disorder being studied or expected progression, signs, or symptoms of the disease/disorder being studied, unless more severe than expected for the participant's condition.
- Medical or surgical procedure (eg, endoscopy, appendectomy): the condition that leads to the procedure is the AE.
- Situations in which an untoward medical occurrence did not occur (social and/or convenience admission to a hospital).
- Anticipated day-to-day fluctuations of preexisting disease(s) or condition(s) present or detected at the start of the study that do not worsen.

#### 10.3.2. Definition of an SAE

**An SAE is defined as any untoward medical occurrence that, at any dose, meets one or more of the criteria listed below:**

**a. Results in death**

**b. Is life-threatening**

The term “life-threatening” in the definition of “serious” refers to an event in which the participant was at risk of death at the time of the event. It does not refer to an event that hypothetically might have caused death if it were more severe.

**c. Requires inpatient hospitalization or prolongation of existing hospitalization**

In general, hospitalization signifies that the participant has been admitted (usually involving at least an overnight stay) at the hospital or emergency ward for observation and/or treatment that would not have been appropriate in the physician's office or outpatient setting. Complications that occur during hospitalization are AEs. If a complication prolongs hospitalization or fulfills any other serious criteria, the event is serious. When in doubt as to whether “hospitalization” occurred or was necessary, the AE should be considered serious.

Hospitalization for elective treatment of a preexisting condition that did not worsen from baseline is not considered an AE.

**d. Results in persistent or significant disability/incapacity**

- The term disability means a substantial disruption of a person's ability to conduct normal life functions.
- This definition is not intended to include experiences of relatively minor medical significance, such as uncomplicated headache, nausea, vomiting, diarrhea, influenza, and accidental trauma (eg, sprained ankle), that may interfere with or prevent everyday life functions but do not constitute a substantial disruption.

**e. Is a congenital anomaly/birth defect**

**f. Is a suspected transmission via a Pfizer product of an infectious agent, pathogenic or non-pathogenic**

The event may be suspected from clinical symptoms or laboratory findings indicating an infection in a participant exposed to a Pfizer product. The terms "suspected transmission" and "transmission" are considered synonymous. These cases are considered unexpected and handled as serious expedited cases by pharmacovigilance personnel. Such cases are also considered for reporting as product defects, if appropriate.

**g. Other situations:**

- Medical or scientific judgment should be exercised by the investigator in deciding whether SAE reporting is appropriate in other situations, such as significant medical events that may jeopardize the participant or may require medical or surgical intervention to prevent one of the other outcomes listed in the above definition. These events should usually be considered serious.
- Examples of such events include invasive or malignant cancers, intensive treatment in an emergency room or at home for allergic bronchospasm, blood dyscrasias or convulsions that do not result in hospitalization, or development of drug dependency or drug abuse.

**10.3.3. Recording/Reporting and Follow-Up of AEs and/or SAEs During the Active Collection Period**

**AE and SAE Recording/Reporting**

The table below summarizes the requirements for recording AEs on the CRF and for reporting SAEs on the CT SAE Report Form to Pfizer Safety throughout the active collection period. These requirements are delineated for 3 types of events: (1) SAEs; (2) nonserious AEs; and (3) exposure to the study intervention under study during pregnancy or breastfeeding, and occupational exposure.

It should be noted that the CT SAE Report Form for reporting of SAE information is not the same as the AE page of the CRF. When the same data are collected, the forms must be completed in a consistent manner. AEs should be recorded using concise medical terminology and the same AE term should be used on both the CRF and the CT SAE Report Form for reporting of SAE information.

Safety Event	Recorded on the CRF	Reported on the CT SAE Report Form to Pfizer Safety Within 24 Hours of Awareness
SAE	All	All
Nonserious AE	All	None
Exposure to the study intervention under study during pregnancy or breastfeeding	All AEs/SAEs associated with EDP or EDB  Note: Instances of EDP or EDB not associated with an AE or SAE are not captured in the CRF	All instances of EDP are reported (whether or not there is an associated SAE)*  All instances of EDB are reported (whether or not there is an associated SAE)**
Environmental or occupational exposure to the product under study to a nonparticipant (not involving EDP or EDB)	None. Exposure to a study non-participant is not collected on the CRF	The exposure (whether or not there is an associated AE or SAE) must be reported***

\* **EDP** (with or without an associated AE or SAE): any pregnancy information is reported to Pfizer Safety using the CT SAE Report Form and EDP Supplemental Form; if the EDP is associated with an SAE, then the SAE is reported to Pfizer Safety using the CT SAE Report Form.

\*\* **EDB** is reported to Pfizer Safety using the CT SAE Report Form, which would also include details of any SAE that might be associated with the EDB.

\*\*\* **Environmental or occupational exposure:** AEs or SAEs associated with occupational exposure are reported to Pfizer Safety using the CT SAE Report Form.

- When an AE or SAE occurs, it is the responsibility of the investigator to review all documentation (eg, hospital progress notes, laboratory reports, and diagnostic reports) related to the event.
- The investigator will then record all relevant AE or SAE information in the CRF.

- It is **not** acceptable for the investigator to send photocopies of the participant's medical records to Pfizer Safety in lieu of completion of the CT SAE Report Form/AE or SAE CRF page.
- There may be instances when copies of medical records for certain cases are requested by Pfizer Safety. In this case, all participant identifiers, with the exception of the participant number, will be redacted on the copies of the medical records before submission to Pfizer Safety.
- The investigator will attempt to establish a diagnosis of the event based on signs, symptoms, and/or other clinical information. Whenever possible, the diagnosis (not the individual signs/symptoms) will be documented as the AE or SAE.

#### Assessment of Intensity

The investigator will make an assessment of intensity for each AE and SAE reported during the study and assign it to 1 of the following categories:

- Mild: A type of AE that is usually transient and may require only minimal treatment or therapeutic intervention. The event does not generally interfere with usual ADL.
- Moderate: A type of AE that is usually alleviated with additional specific therapeutic intervention. The event interferes with usual ADL, causing discomfort, but poses no significant or permanent risk of harm to the research participant.
- Severe: A type of AE that interrupts usual ADL, or significantly affects clinical status, or may require intensive therapeutic intervention.

An event is defined as "serious" when it meets at least 1 of the predefined outcomes as described in the definition of an SAE, NOT when it is rated as severe.

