### **8.3.5. Management of Hypoglycemia**

While GLP-1R agonists typically are not associated with hypoglycemia unless co-administered with anti-diabetic agents that can cause hypoglycemia (such as insulin or sulfonylureas), participants will be monitored for signs and symptoms of hypoglycemia. Blood glucose concentrations may be measured via a glucometer, at investigator discretion.

Any episode of hypoglycemia must be captured on the AE CRF with specific details captured on the HAE Form CRF. For the definition of a hypoglycemic episode and severity categorization see [Section 8.3.5.1](#) below.

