#### **8.3.5.1. Definition and Severity of Hypoglycemic Adverse Event (HAE)**

The investigator must assess any glucose values, if measured, as well as any signs or symptoms reported by the study participant.

HAE is defined as one of the following:

- a. Asymptomatic hypoglycemia: An event not accompanied by typical symptoms of HAE but a glucose value of <70 mg/dL (3.9 mmol/L) using either glucometer (fingerstick blood glucose) at the study site or sponsor approved laboratory (plasma glucose).

- b. Documented symptomatic hypoglycemia: An event during which typical symptoms of HAE are accompanied with a glucose value of  $<70$  mg/dL (3.9 mmol/L), using glucometer (fingerstick blood glucose) at the study site or sponsor approved laboratory (plasma glucose), and the clinical picture includes prompt resolution with food intake, subcutaneous glucagon, or IV glucose.
- c. Probable symptomatic hypoglycemia: An event during which symptoms of HAE are not accompanied by a glucose determination but was presumably caused by a glucose concentration of  $<70$  mg/dL (3.9 mmol/L), and the clinical picture includes prompt resolution with food intake, subcutaneous glucagon, or IV glucose.

Each episode of HAE must be categorized with respect to severity. In order to characterize the event as severe, all 3 criteria below must be met:

1. The participant was unable to treat him/herself. Neurologic impairment, and not the age of the participant, is the explanation for why the participant could not treat him/herself and required the assistance of another person.
2. The participant exhibited at least 1 of the following neurological symptoms:
  - Memory loss;
  - Confusion;
  - Uncontrolled behavior;
  - Irrational behavior;
  - Unusual difficulty in awakening;
  - Suspected seizure;
  - Seizure;
  - Loss of consciousness.
3. Either:
  - If blood glucose was measured and was  $\leq 54$  mg/dL (2.7 mmol/L) using glucometer (or laboratory); or
  - If blood glucose was not measured, the clinical manifestations were reversed by oral carbohydrates, subcutaneous glucagon, or IV glucose.

Events that do not meet all the criteria above for severe HAE are characterized as mild or moderate in severity.

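### A hypoglycemic adverse event is graded mild, moderate or severe by two protocol rules that can disagree, and the glucose cut-off in one of them is printed with mismatched units

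*Protocol*

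**What the plan says.** Protocol Section 8.3.5 places each event on two forms: "Any episode of hypoglycemia must be captured on the AE CRF with specific details captured on the HAE Form CRF". It then refers the reader to Section 8.3.5.1 for the definition of an episode and its severity category. Measuring glucose by glucometer is left to the investigator's discretion.

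Section 8.3.5.1 defines a hypoglycemic adverse event (HAE) by a glucose below 70 mg/dL or, where glucose was not determined, by a presumed value below that level. The relevant type begins: "Documented symptomatic hypoglycemia: An event during which typical symptoms of HAE are accompanied with a glucose value of" less than 70 mg/dL, with prompt resolution after food, glucagon or IV glucose. On severity it says: "In order to characterize the event as severe, all 3 criteria below must be met". The criteria are:

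1. The participant could not self-treat because of neurologic impairment and needed another person's help.
2. At least one listed neurological symptom was present; seizure and loss of consciousness are on the list.
3. Either a measured glucose was at or below 54 "mg/dL (2.7 mmol/L) using glucometer (or laboratory); or" else "If blood glucose was not measured, the clinical manifestations were reversed by oral carbohydrates, subcutaneous glucagon, or IV glucose".

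The default follows: "Events that do not meet all the criteria above for severe HAE are characterized as mild or moderate in severity".

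Appendix 3 (Section 10.3.3, Assessment of Intensity) covers all events: "The investigator will make an assessment of intensity for each AE and SAE reported during the study". It makes no exception for hypoglycemia. Its top grade is: "Severe: A type of AE that interrupts usual ADL, or significantly affects clinical status, or may require intensive therapeutic intervention".

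SAP Section 6.2.1 says that AEs are summarised according to sponsor reporting standards. It does not say which severity field is used.

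**The concern.** Both rules apply to the same event and use the same three grades, but they are built differently. Appendix 3 needs any one of three clinical features for severe and has no glucose threshold. Section 8.3.5.1 needs three criteria jointly, and in the third a measured glucose displaces the evidence of reversal by treatment. Neither document gives one rule precedence, exempts hypoglycemia from Appendix 3, or says that HAE severity and AE intensity are separate variables.

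If the 8.3.5.1 category is copied to the AE page, a seizure at a measured 60 mg/dL is tabulated as mild or moderate beside AEs graded on a different basis. The grade also depends on whether someone took a reading, so better documentation can lower the recorded severity. Hypoglycemia is a named risk in Protocol Section 2.3.1, and TEAEs are part of the secondary safety endpoint. The groups are small, so a single event is visible in a group summary.

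**Working it through.** **Step 1. The 8.3.5.1 rule as logic.** Severe = criterion 1 AND criterion 2 AND [(glucose measured AND at or below the cut-off) OR (glucose not measured AND reversed by treatment)]. Otherwise the event is mild or moderate.

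**Step 2. The cut-off.** With the usual glucose conversion of 18.016 mg/dL per mmol/L (assumed; the documents give none):

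- 54 / 18.016 = 3.0 mmol/L, but 2.7 is printed.
- 2.7 × 18.016 = 48.6 mg/dL, but 54 is printed.
- 70 / 18.016 = 3.89 mmol/L, which agrees with the printed 3.9.

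The protocol's own figures show the same mismatch without an outside factor. The HAE threshold implies 70 / 3.9 = 17.9 mg/dL per mmol/L, whereas the severity cut-off implies 54 / 2.7 = 20.0.

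**Step 3. Apply the rule.** Take an event that meets criteria 1 and 2 (seizure or loss of consciousness, help from another person) and is promptly reversed by IV glucose:

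| Glucose | 8.3.5.1, cut-off 54 mg/dL | 8.3.5.1, cut-off 2.7 mmol/L |
|---|---|---|
| Not measured | Severe | Severe |
| 45 mg/dL | Severe | Severe |
| 49 mg/dL | Severe | Mild or moderate |
| 54 mg/dL | Severe | Mild or moderate |
| 55, 60, 69 mg/dL | Mild or moderate | Mild or moderate |

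In whole mg/dL, the values that meet the HAE definition but are barred from severe are 55-69 on the first reading and about 49-69 on the second.

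**Step 4. Apply Appendix 3 to the same event at 55-69 mg/dL.**

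- Mild: the event should not generally interfere with daily activities. A seizure or loss of consciousness does.
- Moderate: the event should carry no significant or permanent risk of harm. That is hard to say of a seizure or loss of consciousness needing another person's help.
- Severe: interruption of daily activities or a marked effect on clinical status is enough on its own. Both are present.

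Severe is therefore the grade that the wording points to.

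**Step 5. Can 8.3.5.1 stand alone?** It does not say how to separate mild from moderate. A site that follows its default must look elsewhere for that distinction. Appendix 3 is where the protocol defines the two grades, and neither definition fits this event.

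**Step 6. Scale.** One event is 1/6 = 17% of a group, or 1/4 = 25% if Group 4 closes at four participants. These are shares for a single event. The documents give no event rate.

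**The case against.** The best defence is that Section 8.3.5 refers the severity of a hypoglycemic episode to 8.3.5.1, so the specific rule governs the general one. Alternatively, 8.3.5.1 speaks of severity and Appendix 3 of intensity, and details of the episode go on a separate HAE Form, so these may be two fields. Protocol Section 10.1.7 also says that a CRF Completion Requirements document guides form completion; it is not among the documents available here and may settle the matter. Each reading is reasonable, but the protocol and SAP state none of them, and the two readings lead to different entries on the AE page. A request to state the rule therefore stands. A claim that sites will in fact record grades differently would be conjecture.

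Several stronger readings are tempting and are not supported:

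- *Appendix 3 mechanically makes the event severe.* It calls for an investigator's judgement between descriptive categories. Severe is the plain reading for seizure or loss of consciousness, not the output of a threshold.
- *The conflict also runs the other way*, for example brief confusion with no glucose reading, reversed by oral carbohydrate from staff. Criterion 1 requires neurologic impairment that prevented self-treatment, and staff handing over carbohydrate does not establish that. If criterion 1 is met, Appendix 3 may also give severe. This shows possible disagreement only.
- *Serious events could be missed.* Appendix 3 separates seriousness from severity, and Section 10.3.2 lists convulsions among its examples of events for SAE consideration.
- *A named endpoint is compromised.* The secondary endpoint is assessment of TEAEs; severity is not named. SAP Section 6.2 plans no formal safety analyses, and SAP Section 5.1 applies no decision rules.

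**Conclusion.** The point holds as a conflict between two stated grading rules, confined to severe-looking hypoglycemic events with a measured glucose above the criterion-3 cut-off and below 70 mg/dL. Such an event must be mild or moderate under 8.3.5.1 and would be severe on the plain wording of Appendix 3. The range is 55-69 mg/dL if the printed mg/dL figure applies and about 49-69 mg/dL if the printed mmol/L figure applies. The unit mismatch is an inconsistency in its own right and needs no judgement about intensity.

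The consequence is small: descriptive recording and tabulation of TEAE severity. Few events are expected after a single 20 mg dose, and Protocol Section 2.3.1 reports no increased hypoglycemia risk in trials of injectable agents of this class except in combination with drugs such as insulin or sulfonylureas.

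The conclusion assumes that the investigator follows the Appendix 3 wording as written and that no form-completion guidance outside these documents already separates the two ratings. It does not say which severity rule or which glucose figure is right; the documents do not show which was intended.

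**What to change.** The sponsor should:

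1. Reconcile Section 8.3.5.1 with the intensity categories in Appendix 3, and correct the criterion-3 cut-off so that its mg/dL and mmol/L figures agree.
2. State which rating is entered as intensity on the AE CRF and which on the HAE Form. One way is to keep two separately named variables, with the three-criterion result recorded on the HAE Form as a yes/no item for meeting the severe-HAE criteria.
3. State in the SAP the single source from which TEAE severity is tabulated for all AEs, and list the HAE-Form category beside it for hypoglycemic events.

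The cost is a small wording change and one listing column. No additional data are needed, and the management of participants need not change.

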#### Assessment of Causality

- The investigator is obligated to assess the relationship between study intervention and each occurrence of each AE or SAE. The investigator will use clinical judgment to determine the relationship.
- A "reasonable possibility" of a relationship conveys that there are facts, evidence, and/or arguments to suggest a causal relationship, rather than a relationship cannot be ruled out.

- Alternative causes, such as underlying disease(s), concomitant therapy, and other risk factors, as well as the temporal relationship of the event to study intervention administration, will be considered and investigated.
- The investigator will also consult the IB and/or product information, for marketed products, in their assessment.
- For each AE or SAE, the investigator **must** document in the medical notes that they have reviewed the AE or SAE and have provided an assessment of causality.
- There may be situations in which an SAE has occurred and the investigator has minimal information to include in the initial report to the sponsor. However, **it is very important that the investigator always make an assessment of causality for every event before the initial transmission of the SAE data to the sponsor.**
- The investigator may change their opinion of causality in light of -follow-up information and send an SAE -follow-up report with the updated causality assessment.
- The causality assessment is one of the criteria used when determining regulatory reporting requirements.
- If the investigator does not know whether or not the study intervention caused the event, then the event will be handled as “related to study intervention” for reporting purposes, as defined by the sponsor. In addition, if the investigator determines that an SAE is associated with study procedures, the investigator must record this causal relationship in the source documents and CRF, and report such an assessment in the dedicated section of the CT SAE Report Form and in accordance with the SAE reporting requirements.

